Product	
Selection of P2Y12 inhibitor treatment by CYP2C19 allele genotype.
 
The investigational product development is based on the RT-PCR-based detection of normal or loss-of-function alleles of the human cytochrome P450 system 2c19 enzyme encoded by CYP2C19 *2, *3.

Expected use	
Tailoring antiplatelet treatment to optimize MACCEs prevention in high-risk ASCVD patients.

Perspective arm	
A clinical group of patients with ASCVD who require treatment with a P2Y12 inhibitor (including clopidogrel) after PCI for acute myocardial infarction, characterized by a more severe course of the disease and a significantly higher baseline risk of recurrent MACCEs compared with the participants group under the study. The perspective arm is clinically more heterogeneous and requires a different study design.

Duration of the study	
Total duration of the study: 24 months.
 
 
▪ Expected duration of the study activities (from screening/randomization of the first patient to the end of follow-up of the last involved patient): 20 months; 
 
— Patient enrollment period: 8 months;
 
— Follow-up period: 12 months;
 
 
 
▪ Study preparation period: 2 months;
 
 
Study closure period: 2 months.

Follow-up	
Follow-up of study end-points from the start of the study intervention:
 
 
▪ 3 months (<math>\pm 1</math> week);
 
▪ 6 months (<math>\pm 1</math> week);
 
▪ 12 months (<math>\pm 1</math> week);
 
 
Follow-up evaluation within 72 hours in cases of early withdrawal within 12 months from the study for any reason.
 
Reasons for the early withdrawal are defined as:
 
 
▪ Withdrawal by study participant;
 
▪ Non-compliance with treatment intervention;
 
▪ Loss of follow-up;
 
▪ Physician's decision.
 
 
Routine observations of the study cases by the institutional standards and protocols for long-term disease control, as accepted for the real practice of clinical centers enrolling the study participants.

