It is reasonable to assume that 75% of the selected study subjects will complete the study activities in full by 12 months of follow-up after enrollment. A portion of the 25% of patients are expected to drop out of the study for various reasons. Withdrawal by study participants, non-compliance with treatment, loss to follow-up and physician decisions are expected as the possible reasons for the study's non-completion.

Some of the dropped-out study participants will undergo appropriate clinical assessments at the interim follow-up periods (before 3, 6, or 12 months) or at the time of early withdrawal from the study and are therefore also considered a source of study data.

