## **2.5.6 Withdrawal from the Study due to Non-adherence to Treatment**

Non-adherence to the study of treatment with clopidogrel, alternative antiplatelet or other prescribed medication or a patient's decision to avoid or discontinue study procedures is grounds for withdrawal from the study due to non-adherence.

Evaluations for medication non-adherence should be performed at each study-planned follow-up visit using the Brief Medication Use Questionnaire (BMQ) [26].

No single (so-called "gold standard") tool is presented for assessing non-adherence to medication treatment. The highly specific and sensitive BMQ, currently being developed, was selected for the assessment of non-adherence to treatment. Based on characteristics of drug consumption by evaluating (scaling) the responses to nine simple questions and amounts of medication taken "during the past week" and the patient's opinion on the effects, adherence to medication treatment can be calculated. Assessments carried out during the observation period will reveal possible barriers that lead to non-adherence. The results of the assessment of the medication regimen, trust in treatment, and attitude determine the state of repeated or sporadic non-adherence or adherence. To influence the identified factors of non-adherence, the patient will be consulted during the observation period, and it will be possible to overcome sporadic non-adherence cases.

In the event of repeated non-adherence, procedures for withdrawing the patient from the study will be considered.

These procedures include:

- Informing the patient about his/her withdrawal from the study;
- Justification of the decision to withdraw the patient from the study;
- Conducting follow-up assessments of clinical outcomes;
- Clinical examinations are conducted to assess the patient's current condition and safety;

In cases where a patient is withdrawn from the study due to non-adherence to medication treatment during the 3rd, and 6th month of follow-up, a new study subject may be included in the study in his/her place, with allocation to the appropriate experimental or control group. After the 6-month follow-up period, a patient withdrawn from the study should not be replaced by a new study subject.

Withdrawal from the study will be reviewed by the study center investigator, principal investigator, and data management team. The patient will be informed of the non-adherence case and the decision to withdraw from the study.

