The investigator will describe and analyze the reason for the study participant's early withdrawal, which is part of the routine medical records. An adverse clinical event will be registered in the study data form.

The investigator will inform the study participant of the decision to withdraw from the study early and about further follow-up and treatment measures.

Patient data collected before withdrawal will be used for study purposes, with confidentiality, following the procedures provided and the terms presented to the patient in the informed consent form.

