### Appendix 3. Indicators for evaluating the effectiveness of the study product

Indicator	Statistical Analysis
Number of study participants (n) with genotype of heterozygous and homozygous mutation of CYP2C19 *2, *3 alleles	Counting: Number of study participants with wt/mut or mut/mut alleles by CYP2C19 *2, *3 genotyping
Percentage (%) of study having heterozygous or homozygous mutations of CYP2C19 *2, *3 genotype	Numerator: Number of study participants with wt/mut or mut/mut alleles by CYP2C19 *2, *3 genotyping Denominator: Total number of experimental arms study participants, tested for CYP2C19 genotype
The rate (percentage - %) of death from any cause among study participants	Numerator: Number of study participants dead from any cause Denominator: Total number of study participants
The rate (percentage - %) of death from any cause among 'normal metabolizer' study participants	Numerator: Number of 'normal metabolizer' study participants dead from any cause Denominator: Total number of 'normal metabolizer' study participants
The rate (percentage - %) of death from any cause among 'passive metabolizer' study participants	Numerator: Number of 'passive metabolizer' study participants dead from any cause Denominator: Total number of 'passive metabolizer' study participants
The rate (percentage - %) of death from any cause among 'unspecified metabolizer' study participants	Numerator: Number of 'unspecified metabolizer' study participants dead from any cause Denominator: Total number of 'unspecified metabolizer' study participants
The hazard ratio (HR) of death from any cause for 'normal metabolizer' study participants vs 'unspecified metabolizer' study participants	Numerator: the hazard rate from any cause of death of 'normal metabolizer' study participants, calculated as the proportion of any cause of death among 'normal metabolizer' study participants Denominator: the hazard rate from any cause of death of 'unspecified metabolizer' study participants, calculated as the proportion of any cause of death (%) among 'unspecified metabolizer' study participants

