The hazard ratio (HR) of death from any cause for study participants of 'normal metabolizer' and 'passive metabolizer' vs 'unspecified metabolizer' study participants	Numerator: the hazard rate from any cause of death of 'normal metabolizer' study participants, calculated as the proportion of any cause of death among 'normal metabolizer' and 'passive metabolizer' study participants Denominator: the hazard rate from any cause of death of 'unspecified metabolizer' study participants, calculated as the proportion of any cause of death (%) among 'unspecified metabolizer' study participants
The relative risk (RR) of developing death from any cause for 'normal metabolizer' study participants' arm vs 'unspecified metabolizer' study participants' arm	Numerator: the probability of developing death from any cause in the 'normal metabolizer' study participants arm, calculated as the number of 'normal metabolizer' study participants dead from any cause divided by the sum of the number of 'normal metabolizer' study participants dead from any cause and number of 'normal metabolizer' study participants not dead from any cause; Denominator: the probability of developing death from any cause in the 'unspecified metabolizer' study participants' arm, calculated as the number of 'unspecified metabolizer' study participants dead from any cause divided by the sum of the number of 'unspecified metabolizer' study participants dead from any cause and number of 'unspecified metabolizer' study participants not dead from any cause;
The relative risk (RR) of developing death from any cause for aggregated 'normal metabolizer' and 'passive metabolizer' study participants' arms vs 'unspecified metabolizer' study participants' arm	Numerator: the probability of developing death from any cause in the aggregated 'normal metabolizer' and 'passive metabolizer' study participants arm, calculated as the aggregated number of 'normal metabolizer' and 'passive metabolizer' study participants dead from any cause divided by the sum of the aggregated number of 'normal metabolizer' and 'passive metabolizer' study participants dead from any cause and aggregated number of 'normal metabolizer' and 'passive metabolizer' study participants not dead from any cause;

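### Appendix 3 divides recorded events by everyone in the arm although up to 25% may not complete, so unobserved time after withdrawal counts as event-free in the 12-month rates

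*Combined protocol and SAP*

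**What the plan says.** **Completion.** Section 2.4.2: "It is reasonable to assume that 75% of the selected study subjects will complete the study activities in full by 12 months". It adds that a portion of the remaining 25% will drop out, so 25% is an upper figure for dropout.

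**Rates and AB.** Appendix 3 divides the number with the event by "Total number of study participants" overall and, within an arm, by for example "Total number of 'normal metabolizer' study participants". AB is the difference between two such rates.

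**RR and RB.** The RR for all-cause death puts the deaths over a denominator that adds two counts: "number of 'normal metabolizer' study participants dead from any cause and number of 'normal metabolizer' study participants not dead from any cause". RB is 1 minus RR. Unknown status has no place in this sum.

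**HR.** Section 2.6.3 plans Cox regression. Appendix 3 defines the HR as one crude proportion divided by another.

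**What is known about people who leave.** The Synopsis requires "Follow-up evaluation within 72 hours in cases of early withdrawal within 12 months from the study for any reason", and the visit schedule in Appendix 2 includes endpoint evaluation at that visit. Section 2.4.2 says some dropouts are assessed at interim visits or "at the time of early withdrawal from the study and are therefore also considered a source of study data". Section 3.3: "Patient data collected before withdrawal will be used for study purposes".

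**After an event.** Section 3.2.6 withdraws a participant once a MACCE or AAME is registered, and section 3.3 says that planned follow-up is then not needed. Section 3.2.7 lets the IRB recommend either further follow-up or withdrawal. Section 3.2.1 counts minor bleeding and a change of P2Y12 inhibitor among the AAMEs.

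**Replacement.** For non-adherence withdrawals at the month 3 and month 6 follow-up, section 2.5.6 allows that "a new study subject may be included in the study in his/her place, with allocation to the appropriate experimental or control group".

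The documents define no analysis set, no rule for unknown month-12 status and no censoring rule for the rates, RR, RB or AB.

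**The concern.** A crude proportion estimates 12-month risk only if everyone in the denominator is followed for 12 months or until the event. Here a sizeable share may not be. A participant who leaves at month 4 without an event stays in the denominator for the whole year, and anything that happens in the other eight months is not recorded. The rate comes out too low, and so does AB.

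The gap matters most for death, the primary endpoint. A minor bleed or a drug switch can end planned observation, so a later death may go unrecorded. The comparison between arms is also exposed if withdrawal differs by arm. That is plausible, because treatment is known after genotyping (section 2.5.4) and the loss-of-function arm receives different drugs, but the documents give no dropout figures by arm.

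**Working it through.** **Inputs from the plan.** Total 240; allocation 1:2, so 80 control and 160 guided; completion 75%; follow-up 12 months; MACCE probability 1–10% (section 3.2.1). The plan's sample sizes reproduce to within 3%: 219 against the stated 221, 247 against 251, and a mean of the two stated sizes of 236 against 240. I therefore take 240 as given. The plan states no expected rate under the Appendix 3 formulas to reproduce.

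**Assumptions.** Dropout timing, dropout by arm, and an event risk that is steady over the year are mine.

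**1. Understatement of the rate.** Let a share d leave without an event and let u be the average fraction of the year not observed. Recorded risk ≈ true risk × (1 − d × u).
- Exits spread evenly (u = 0.5): 1 − 0.25 × 0.5 = 0.875, which is 12.5% too low.
- All exits at month 3 (u = 0.75): 1 − 0.25 × 0.75 = 0.8125, which is 19% too low.

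A constant-hazard calculation agrees. With dropout spread over the year, a true 1%, 5% or 10% is recorded as 0.87%, 4.35% or 8.71%, about 13% too low. At a true 5%, the recorded rate is 3.75% if all leave on day 0, 4.07% at month 3, 4.38% at month 6 and 4.69% at month 9, so 25% to 6% too low.

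**2. Effect on AB.** With equal dropout, AB shrinks by the same factor. A hypothetical 10% against 5% gives a true AB of 5 points, recorded as 5 × 0.875 = 4.4 or 5 × 0.8125 = 4.1.

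**3. Effect on RR, people of unknown status counted as without event.**
- Equal, non-informative dropout: the factors cancel and a true 1.00 stays 1.00.
- Hypothetical 30% guided against 15% control: (160 × 0.30 + 80 × 0.15)/240 = 60/240 = 25% overall, as in the plan. Even spread: (1 − 0.30 × 0.5)/(1 − 0.15 × 0.5) = 0.85/0.925 = 0.92. All at month 3: (1 − 0.30 × 0.75)/(1 − 0.15 × 0.75) = 0.775/0.8875 = 0.87.
- Reversed (15% guided, 30% control), even spread: 0.925/0.85 = 1.09.

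**4. Why the missing class matters for RR.** If people of unknown status were left out of both terms instead, the even-spread 30% against 15% case gives (0.85/0.70)/(0.925/0.85) = 1.214/1.088 = 1.12. The same data give 0.92 or 1.12 depending on a rule that is not written.

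**5. Replacements.** Arm of 80, true risk 5%, 20 leaving at month 6.
- No replacement: 3.506/80 = 4.4%.
- All 20 replaced and both groups kept: 4.506/100 = 4.5%.

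Replacements bring their own follow-up and do not lower the rate further.

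**The case against.** Several points on the other side are sound.

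- **Events up to withdrawal are captured.** A reader might infer that every dropout is scored as having no event. The documents do not support that: there is an exit evaluation, earlier data are used, and people withdrawn because of a MACCE are event-positive for it. Only the time after withdrawal is lost.
- **25% is an upper figure.** Part of it consists of people who already had an event, so 12.5% and 19% are upper-end values for their assumed timing.
- **The RR text does not divide by all participants.** It uses with-event plus without-event. For cardiovascular and non-cardiovascular death, the normal-metabolizer side adds only those alive, while the comparator side adds everyone without that cause of death. For RR and RB the fault is an absent rule, plus this mismatch.
- **Replacement.** A reader might infer that replacements inflate the denominator and dilute the rate. The wording could equally mean substitution, and step 5 shows no extra dilution even if both are kept. What stands is that the new person's arm appears to follow from the person replaced, and that nobody has said whether the replaced person stays in the totals. Removing them would be an exclusion after randomisation.
- **Cox regression can censor.** True, but Appendix 3 redefines the HR without person-time, and the rates, AB, RR and RB never censor.
- **The RR shift is small beside sampling error.** At 5% risk there are about 8 against 4 events, and the 95% CI around a null RR runs from roughly 0.31 to 3.2. At 10% it is about 0.45 to 2.2. This limits the practical weight of the RR point; it does not make the rates correct.

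**Conclusion.** The concern holds for the rates and AB, where the written formula itself produces the error, and for the HR, where Appendix 3 contradicts section 2.6.3. For RR and RB the defect is that unknown status has no rule.

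If the full 25% leave without an event, 12-month risk is understated by about 12.5% with even exits and 19% with all exits at month 3, given a steady event risk and non-informative dropout. A smaller event-free loss gives a proportionally smaller error.

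It would go too far to say that the plan biases the RR. That needs unequal or informative dropout, and no dropout rates by arm are given. The values 0.92 and 0.87 belong to an assumed 30% against 15%, and the direction reverses if control loses more. For replacements, the finding is an undefined analysis set, not a demonstrated numerical effect.

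**What to change.** - **Analysis set.** Analyse all randomised participants as randomised. Keep replaced participants in the set and report replacements separately.
- **Rates.** Replace the crude proportions in Appendix 3 with Kaplan-Meier 12-month risk for all-cause death and for the composites that include it (MACCE, NACE). Use cumulative incidence with death as a competing event for cardiovascular death and the non-fatal events, and likewise for MACE, which counts only cardiovascular death.
- **RR, RB, AB.** Derive them from those estimates. This also removes the mismatched denominators for cause-specific death.
- **HR.** Use the Cox HR of section 2.6.3 and delete the ratio of proportions from Appendix 3.
- **Follow-up.** Collect month-12 vital status for withdrawn participants who have not refused further contact. Reconcile sections 3.2.6, 3.2.7 and 3.3 on what observation continues after an event.
- **Sensitivity analysis.** Kaplan-Meier and Cox assume non-informative censoring, which is doubtful when people leave for non-adherence or adverse events. Add a worst-case analysis and a range of assumed risks for those of unknown status.

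**Cost.** Standard software and a short month-12 status check. Confidence intervals should be slightly wider (not computed here). The status check settles all-cause death only; cause of death and non-fatal events after withdrawal stay unknown, which is why the sensitivity analysis is still needed.

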#### **2.4.3 Inclusion Criteria**

Inclusion criteria define the clinical model according to which the study subject will be selected. The criteria will equalize cardiovascular risk disease/condition and co-morbidities that may distinguish and exclude CAD severity.

A patient will be selected for the study participation if they meet all of the following inclusion criteria:

- Participants of both sexes aged between 35-80 years are eligible for the study.

[and]

- Diagnosed with chronic coronary artery disease;

[and]

- Completed informed consent form for participation in the study;

[and]

- Undergone elective PCI within the last 12 weeks without procedure-related complications; or the clinical challenge is to de-escalate post-PCI antiplatelet treatment from an alternative P2Y12 inhibitor to clopidogrel.

[and]

- LVEF $\geq$ 38% after index PCI;

Atherosclerotic coronary artery lesion confirmed by coronary angiography and coronary artery stenting performed within 12 weeks without clinically significant procedural complications are determined by the results of relevant PCI. De-escalation of antiplatelet treatment from an alternative P2Y12 inhibitor to clopidogrel can be easily detected by the prescription order from routine clinical practice.

Complementary, this inclusion criterion also represents clinical evidence of CAD medication treatment.

The selected participant should be characterized by echocardiographically confirmed normal or clinically mild left ventricular systolic dysfunction or preserved systolic function after the index PCI. Assessment of systolic function should be assessed by the standard echocardiographic measurements of left ventricular ejection fraction. Echocardiography should be performed as part of the screening measures of the potential study participant before randomization.

#### **2.4.4 Exclusion Criteria**

Exclusion criteria are defined as diseases, clinical conditions, risks or treatment limitations, and contraindications that increase the severity and risks of the study cases. These conditions may have

additional negative prognostic effects on the study subject's disease/condition, interfere with the development of study endpoints, or alter the effectiveness of the treatment interventions included in the study.

Exclusion criteria are used to identify and exclude potential study participants with clinical severity characteristics to ensure homogeneity of treatment effects. They also prevent bias, confounding, and unintended effects.

The use of criteria ensures the safety of subjects in the study by identifying diseases/conditions that require clinical observation, evaluation, and treatment measures other than those specified in the study.

Any of the following should be considered as exclusion criteria from the study:

- Concomitant using of potent CYP3A4 or CYP2C19 inhibitors;
- Clinical obesity, BMI - 40 kg/sq.m or more;
- Type 1 diabetes mellitus;
- Poorly controlled type 2 diabetes mellitus, Hba1c - 9% or more;
- Acute Myocardial Infarction;
- Coronary artery bypass grafting was performed within the last 12 weeks.
- Valvular heart disease due to dysplasia, connective tissue disorders, or inflammatory disorders, or valvular disorders requiring cardiac surgery;
- History of severe hepatic impairment;
- Severe chronic kidney disease;
- Clinically important leucopenia, lymphopenia, thrombocytopenia or thrombocytosis;
- History of hemorrhagic diathesis or coagulopathy;
- An active or an obvious threat of bleeding (including GI bleeding):
- Bleeding within the past 6 months that required hospitalization;
- Blood transfusion during the past 6 months or its refusal;
- History of intracranial hemorrhage;
- Cardiac or non-cardiac degenerative disease, including: cardiomyopathy, restrictive lung disease, or neurodegenerative diseases;
- Malignant tumor (cancer) that limits life expectancy to less than one year;
- Current chemotherapy or immunosuppressive therapy;
- Ongoing immunosuppression or immunosuppressive conditions;
- Pregnancy or lactation period;
- Any disease/condition for which control is not achieved;
- Personal (patient/physician dependent) or health care system-related circumstances that can restrict or limit any study procedures or operations.

Concomitant use of other drugs that inhibit CYP3A4 or CYP2C19 with clopidogrel may reduce the expected positive effects of treatment and induce negative ones, since the hepatic metabolism of clopidogrel is also mainly mediated by CYP2C19 and to a lesser extent by CYP3A4. The concomitant use of drugs that inhibit CYP3A4 or CYP2C19 can be assessed by reviewing the patient's medical history. Their use is prohibited during the study and must be discontinued 2 weeks before enrollment, otherwise, it will constitute an exclusion criterion from the study. Below is a list of drugs that inhibit CYP3A4 or CYP2C19 and their use is prohibited during the study period. If the use of these medications is necessary, the patient will be considered for withdrawal from the study.

— CYP3A4 inhibitors:

Omeprazole, clarithromycin, erythromycin, diltiazem, itraconazole, ketoconazole, ritonavir, verapamil, grapefruit;

— CYP2C19 inhibitors:

Omeprazole, fluvoxamine, ticlopidine, efavirenz, chloramphenicol, fluoxetine, delavirdine, gemfibrozil, stiripentol, bortezomib.

The PPI of choice for patients included in the study is pantoprazole. However, according to the CPIC CYP2C19 genotype-based PPI dosing guidelines and recommendations [25], carriers of CYP2C19 \*2, \*3 LOF alleles are at increased plasma concentrations of this PPI and increased risk of toxicity with prolonged treatment (>12 weeks). Despite the expected increase in treatment efficacy, the drug dose should be reduced by 50% for use >12 weeks and continued monitoring for maintenance of efficacy.

BMI is determined by calculating the results of simple anthropometry.  $BMI \geq 40 \text{ kg/m}^2$  defines clinical obesity/fatty states. They are considered an independent risk factor for repeated MACCE in CAD cases. Prevention of this risk factor requires consistent, intensive measures of lifestyle changes (diet, physical activity) and drug treatment for at least 6-12 months, during which it is impossible to achieve results during the study inclusion and observation period. The excess of risks due to this factor during the study may be an important reason for the dispersion of the study effects. Including patients with this clinical characteristic in the study group, only with the drug treatment provided by the study, would be ethically unjustified. Accordingly,  $BMI \geq 40 \text{ kg/m}^2$  is an important exclusion criterion from the study.

Type 1 Diabetes mellitus and uncontrolled or poorly controlled type 2 diabetes mellitus are considered important independent risk factors for recurrent MACCE in CAD cases. High glycemia levels will act as an important cause of excess risk and may cause dispersion of effects in the course of the study.

Additionally, randomization of study participants with uncontrolled glycemia without CYP2C19 genotyping (control arm) and the possible presence of CYP2C19 \*2, \*3 LOF allele genotype cannot be assessed. Such study participants will be at higher risk than participants randomized in experimental arms, which would be unjustified, allow unequal risk in the study and raise ethical concerns.

Clinical evidence of Type 1 Diabetes mellitus can be assessed by obtaining the patient's medical history. Uncontrolled or poorly controlled diabetes mellitus can be specifically defined as a history of diabetes mellitus, clinical evidence of inadequate glycemic control, elevated glycated hemoglobin ( $HbA1c \geq 9\%$ ), or clinical evidence of vascular complications of diabetes.

Patients with type 2 diabetes mellitus may be included in the study if the results of the screening test:

- $HbA1c < 9\%$ ;  
[and]  
▪ are receiving optimal medical treatment to control glycemic levels;  
[and]  
have no evidence of progressive vascular complications of diabetes other than CAD;

Such assessment results should also be demonstrated by the 6th and 12-month follow-up of the study. If these key criteria for diabetes control are not met, the subject should be withdrawn from the study early after appropriate investigations have been conducted.

Acute myocardial infarction, valvular heart disease, or previous valvular heart surgery are high-risk conditions for recurrent MACCE.

Interstitial lung disease, neurodegenerative diseases, agranulocytosis (leukopenia, lymphopenia), pancytopenia, thrombocytopenia or thrombocytosis, and any other uncontrolled disease or clinical condition in the course of CAD are associated with high risks of other serious clinical conditions and a poor prognosis.

These diseases/conditions may serve as important causes of biases and confounding effects during analyzing study outcomes. They can be easily identified as part of screening measures based on the patient's medical history and the results of routine clinical examinations.

Certain conditions should be routinely considered for the determination of study exclusion criteria.

Thrombocytopenia is a condition that increases the risk of bleeding complications and thrombotic thrombocytopenic purpura (TTP) during treatment with clopidogrel or an alternative P2Y12 inhibitor. Therefore, thrombocytopenia is considered an important limitation of antiplatelet therapy and an exclusion criterion of the study. This important side effect of treatment can be clinically manifested by thrombocytopenia, microangiopathic hemolytic anemia (schistocytosis - fragmented erythrocytes), neurological symptoms, renal failure, and fever.

Treatment with an NSAID and warfarin is a significant limitation of treatment with clopidogrel or an alternative P2Y12 inhibitor and is an exclusion criterion from the study. Nonsteroidal anti-inflammatory drugs (NSAIDs) are associated with a significant increase in the risk of gastrointestinal bleeding when used concomitantly with clopidogrel or alternative P2Y12 inhibitors. This effect is particularly pronounced when NSAIDs are used in the setting of DAPT.

The interaction of warfarin and clopidogrel does not change the pharmacokinetic properties of the drugs, since during the process of liver metabolism, they are substrates of different enzyme systems (CYP2C9 and CYP2C19, respectively) and do not act by reducing INR in cases of long-term use of warfarin. However, the simultaneous use of warfarin and clopidogrel or alternative P2Y12 inhibitors during treatment critically increases the risk of clinically significant bleeding (gastrointestinal or intracerebral), since they independently suppress coagulation.

Hemorrhagic diathesis, coagulopathy, significant bleeding within the past 6 months, blood transfusion within the past 6 months (or refusal of blood transfusion), active gastrointestinal bleeding or threat of bleeding, and a history of intracranial hemorrhage pose clinical conditions that determine a high risk of recurrent bleeding complications. Therefore, these conditions carry an obvious threat of recurrent bleeding events during treatment with P2Y12 inhibitors, clopidogrel or alternatives, due to inhibiting platelet aggregation. Platelet inhibition occurs throughout their life cycle (7-10 days), and in the event of bleeding, simply stopping the drug will not have a significant effect on pro-coagulation treatment. However, due to the short half-life of the active metabolite of clopidogrel, hemostasis can be restored by infusion of exogenous platelets. The effects of platelet transfusion are significantly reduced within 4 hours of a loading dose of clopidogrel and within 2 hours of a maintenance dose.

When conducting antiplatelet therapy with clopidogrel, prasugrel or ticagrelor, it is necessary to take into account the following conditions that are not direct contraindications, but which nevertheless determine important limitations.

After surgical operations, the expected antiplatelet effects in response to treatment with P2Y12 inhibitors are undesirable. Therefore, treatment with P2Y12 inhibitors should be discontinued at least 5 days before surgery and should be resumed as soon as the operative risk of bleeding has decreased.

In patients with moderate and severe renal insufficiency (creatinine clearance from 30 ml/min to 60 ml/min and <30 ml/min, respectively), clopidogrel reduces the effects of ADP-induced platelet aggregation by an average of 25%. Such effects are associated with an increased risk of thrombosis despite clopidogrel treatment. Increasing the dose of clopidogrel to reduce the risk of thrombotic complications is unreasonable and significantly increases the risk of bleeding and TTP. Therefore, cases of moderate and severe chronic kidney disease are exclusion criteria from the study.

In cases of liver failure, the effects of clopidogrel treatment on ADP-induced platelet aggregation are the same as in healthy individuals. However, in conditions of liver failure, due to the addition of the effects of impaired metabolism of clotting proteins (factors), clopidogrel treatment causes more profound hemostasis disorders, and in cases of thrombocytopenia, it leads to a significantly increased risk of TTP. The risk of major bleeding increases. Therefore, clinically significant liver diseases are exclusion criteria from the study.

Malignant tumor (cancer), ongoing chemotherapy or immunosuppressive therapy, as well as immunosuppressive or autoimmune disease and any uncontrolled disease, constitute clinical conditions under which observation of patients according to the study plan will be impossible, or these diseases/conditions may cause a severe outcome of the clinical case under study. Such conditions may serve as objects of biases and confounding effects when analyzing study outcomes. In this regard, malignant tumor (cancer), ongoing chemotherapy or immunosuppressive therapy, as well as immunosuppressive or autoimmune disease and any uncontrolled disease are considered exclusion criteria from the study.

Under the special clinical discussion, certain diseases/conditions could not be routinely considered as study exclusion criteria:

- A prior myocardial infarction >3 months, or old myocardial infarction, is not considered an exclusion criterion if the clinical characteristics of the study participants meet the inclusion criteria.
- Cases of valvular heart disease that meet the inclusion criteria and are not caused by rheumatic heart disease, and valvular heart disease that does not require cardiac surgery, could not be considered for exclusion from the study.
- Cases of obstructive/interstitial lung disease that meet the inclusion criteria and are not treated by systemic immunosuppressive drugs, or do not show a clinically significant immunosuppressive condition and do not have a life expectancy <1 year due to the disease, could not be considered for exclusion from the study.

